12 CRITERIA FOR EVALUATION AND ENDPOINT

12.1 Primary Objective

The number of days from surgery to the initiation of adjuvant radiation will be retrospectively collected and compared between Arm 1 and Arm 2. The day of surgery will be considered day 0 and the number of days will be counted until the first dose of adjuvant radiation.

12.2 Secondary Objectives

12.2.1 Safety

Routine safety will be evaluated from the results of reported signs and symptoms during study visits. Safety will be evaluated from scheduled physical examinations, vital sign measurements, and clinical laboratory test results collected at the participant's visits

Physical Examination

Complete and symptom-directed physical examinations will be performed by a licensed physician (or physician's assistant or nurse practitioner).

Vital Signs

Vital signs will include blood pressure, respiratory rate, pulse rate, and temperature.

Safety Laboratory Determinations

Laboratory evaluations will be performed as noted in the Schedule of Events.

12.2.2 Pain Control and Management

Pain control and management will be compared between Arm 1 and Arm 2 and will be gauged through:

- Patient-reported subjective pain scores will be recorded on the visual analog scale of pain intensity averaged over a week at rest, with a swallow, and with a cough.
- Questionnaires focused on patient satisfaction with pain control.
- Narcotic consumption in daily total morphine equivalents averaged over a week collected from patient recorded opioid use throughout study therapy.

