1.2 Secondary Objective

- To assess overall pain control and management for patients on celecoxib compared to placebo.

Secondary Endpoints:

- Subjective pain scores on the visual analog scale of pain intensity averaged over a week at rest, with a swallow, and with a cough.
- Patient satisfaction with pain control questionnaire.
- Narcotic consumption in daily total morphine equivalents averaged over a week.

- To assess functional outcomes for patients on celecoxib compared to placebo

Secondary Endpoints: Current activity level and swallowing capabilities, including food and liquid variety and assessment of G tube utilization.

- To assess the effect of celecoxib therapy on Quality of Life (QoL) compared to placebo.

Secondary Endpoint: completion of quality of life questionnaires EORTC QLQ-H&N43 and MDASI-HN as per the schedule of events.

- To assess the average number of treatment days missed during adjuvant radiation for patients on celecoxib compared to placebo.

Secondary Endpoint: the number of treatment days missed or delayed during adjuvant radiation.

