7.3.3 Duration of Therapy

Subjects will receive twice-daily dosing of 200 mg celecoxib three to seven days prior to surgery and continue twice-daily dosing until the completion of adjuvant radiation. The total duration of treatment should be approximately four to six months.

Subjects will receive celecoxib treatment until intolerable toxicity, completion of adjuvant radiation, or six months.

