⁷ Appendix 8: Treating Investigator Patient Assessment Guidance to be filled out by the treating investigator at the time of physical exam.

⁸ See Appendix 8: Treating Investigator Patient Assessment Guidance

⁹ Hematology to include CBC with platelets and differential.

¹⁰ Chemistry to include a complete metabolic panel (CMP).

¹¹ All women of child-bearing potential must have a negative pregnancy test 7 days prior to surgery.

¹² Only required if there is a known history of HIV, hepatitis B, or hepatitis C to confirm eligibility.

¹³ The radiation oncology consultation should be completed prior to registration if possible. This will include a discussion of the indications for adjuvant radiation treatment, a typical treatment course, and the anticipated/possible side effects so the subjects know what to expect if enrolled on trial.

¹⁴ Prior to surgery, the surgical team (physicians, nursing staff, pharmacy, etc.) will be notified about the patients involvement in the trial to ensure standard of care celecoxib and other prohibited therapies are not inadvertently administered.

¹⁵ Patients will complete 1 to 7 days of study therapy prior to surgery and continue twice daily dosing until the last radiation session.

¹⁶ Appendix 3: MDASI Head and Neck Cancer, Appendix 4: EORTC QLQ-H&N43, Appendix 5: Pain Satisfaction Questionnaire, and Appendix 7: Visual Analog Scale for Pain to be completed within 1 month of the scheduled time-points.

¹⁷ Appendix 6: Pre-treatment Questionnaire to be completed at the pre-operation visit.

¹⁸ Patients will be required to record all opioids taken for pain management on Appendix 4: Pain Management Diary while at home. Diary does not need to be maintained during admission post-surgery but should be started when study therapy is started and continue until completion of study therapy.

¹⁹ 5 weeks (\pm 7 days) post-operation the study team will contact the patient to review their medication diary, adverse events, and analgesic use record. If not returning to the study site at this time point, patients will be asked to fax or scan and email their Patient Dosing Diary and Pain Management Diary use records for the study team for review to ensure timely review of study drug compliance.

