11.4 Analgesic Use Record

All patients will be required to keep a diary of all opioids used for pain management during the trial. Patients should be instructed to record all opioid use from the start of study therapy to the end of study therapy. This information will be converted to Oral Morphine Equivalents (OME) and recorded in the eCRF.

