13.4 Statistical Analyses

Appropriate descriptive statistics will be reported for all study variables, stratified by treatment arm. These will include mean, standard deviation and 95% confidence interval for continuous study variables. For categorical study variables the descriptive statistics will include counts, proportions and 95% binomial confidence intervals.

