13.4.2 Secondary endpoint

The secondary endpoints fall into two categories for statistical analysis:

- A. Opioid use, subjective pain score, functional assessment of swallow, number of treatment days missed or delayed, and quality of life questionnaire (EORTC QLQ-H&N43 and MDASI-HN) individual items and summary scales.

Each of the endpoint variables in Category A will be analyzed using a Gaussian mixed effects regression model. The model will contain fixed effects for treatment arm and provider and a nested random effect for patient within provider. The mean difference between treatment groups and a 95% confidence interval will be calculated from the model.

- B. G tube required (Y/N)

G tube use will be analyzed using a mixed effects logistic regression model. The model will contain fixed effects for treatment arm and provider and a nested random effect for patient within provider. An odds ratio between treatment groups and a 95% confidence interval will be calculated from the model.

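### Opioid use: section 13.4.2 names no analysis weeks and its model has no week, visit or phase term, so pooling the whole course would mix any drug effect with a change in phase mix

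*Combined protocol and SAP*

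**What the plan says.** Section 1.2 gives the endpoint as "Narcotic consumption in daily total morphine equivalents averaged over a week" and does not say which week. Section 12.2.2 adds the source of the data: "Narcotic consumption in daily total morphine equivalents averaged over a week collected from patient recorded opioid use throughout study therapy".

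The diary covers the whole of study therapy (section 11.4): "Patients should be instructed to record all opioid use from the start of study therapy to the end of study therapy". There is one gap, in the notes to Table 4: "Diary does not need to be maintained during admission post-surgery". Under section 7.3.3 patients "continue twice-daily dosing until the completion of adjuvant radiation", so the length of the diary depends on when radiation starts, which is the primary endpoint.

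Opioid use is in Category A of section 13.4.2: "Each of the endpoint variables in Category A will be analyzed using a Gaussian mixed effects regression model". The model is then described: "The model will contain fixed effects for treatment arm and provider and a nested random effect for patient within provider". The output is a mean difference between arms with a 95% confidence interval. Table 4 lists the analgesic record at the pre-operation, post-operation, mid-radiation and end-of-treatment visits, but section 13.4.2 does not tie the opioid endpoint to those visits.

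**The concern.** Opioid use after head and neck surgery is unlikely to be constant. It may be high soon after the operation, lower while the patient waits for radiation, and higher again during radiation. If celecoxib works as hypothesised, celecoxib patients lose about two weeks of waiting time and keep the other phases. A model without a time or phase term, fitted to weekly values from the whole course, cannot separate this change of mix from an effect of the drug on opioid use.

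If waiting-period use is low, the pooled comparison makes celecoxib look worse on opioids the better it does on the primary endpoint, and a true saving is understated. More patients would not remove that shift. Which weeks enter the model can therefore move the result, and the plan leaves the choice open.

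**Working it through.** **Inputs from the documents.** Mean days to radiation 72 and 57.2, SD 16.2, 20 per arm, alpha 0.05 (section 13.2). Lead-in of 1 to 7 days (section 7.1; the three to seven days in section 7.3.3 lie inside this range). Total therapy about 4 months (Study Summary).

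**Assumptions.** A 4-day lead-in (midpoint) and 43 days of radiation, which is what remains of about 4 months on placebo: 119 - 4 - 72 = 43. Opioid use by phase is not in the documents, so several profiles are tried.

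**1. The plan's own figure.** Difference 72 - 57.2 = 14.8 days. The noncentrality is (14.8/16.2) × √(20/2) = 2.89. A two-sided t-test then has power 0.804, which reproduces the stated 80%.

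**2. Time on therapy.** Lead-in + days to radiation + radiation days:
- Placebo: 4 + 72 + 43 = 119 days. Radiation share 43/119 = 36.1%.
- Celecoxib: 4 + 57.2 + 43 = 104.2 days. Radiation share 43/104.2 = 41.3%.
- Shortening: 14.8/119 = 12.4%. With a lead-in of 1 to 7 days, radiation of 35 to 49 days and a control mean of 72 or 72.8, it runs from 11.6% to 14.3%.

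**3. Effect on a pooled mean.** Let m be the placebo course mean and w the daily use in the late waiting period, with identical use by phase in both arms. Removing 14.8 waiting days gives a celecoxib mean of (119m - 14.8w)/104.2. The difference from m is (14.8/104.2)(m - w) = 0.142(m - w). Its sign is that of m - w: against celecoxib if late waiting use is below the course mean, zero if the two are equal, and in its favour otherwise.

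**4. Size under assumed profiles.** No true drug effect. The early phase lasts to day 21 after surgery. Pre-operative use is 10 mg/day (5 in the last row). Eight inpatient days are unrecorded, except in the two rows marked *.

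| Early / late waiting / radiation (mg/day) | Placebo mean | Celecoxib mean | Celecoxib minus placebo |
|---|---|---|---|
| 60 / 5 / 60 | 32.9 | 37.2 | +4.3 |
| 40 / 5 / 40 | 22.8 | 25.6 | +2.7 |
| 50 / 10 / 30 * | 24.3 | 26.3 | +2.0 |
| 50 / 10 / 30 | 22.4 | 24.3 | +1.9 |
| 30 / 20 / 30 | 24.7 | 25.4 | +0.7 |
| 20 / 20 / 20 * | 19.7 | 19.6 | -0.05 |
| 40 / 20 / 10 | 18.1 | 17.8 | -0.3 |
| 60 / 20 / 5 | 18.3 | 18.1 | -0.3 |

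Example, second row. Placebo: (4×10 + 13×40 + 51×5 + 43×40)/111 = 2535/111 = 22.8. Celecoxib: (4×10 + 13×40 + 36.2×5 + 43×40)/96.2 = 2461/96.2 = 25.6.

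**5. The same data by phase.** With identical use in each phase, a contrast within a phase, or between values taken at the same visit, is 0 whatever the start date of radiation.

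**The case against.** The strongest reply is that the plan does not average over the whole course. Both definitions say a weekly average, and the words about study therapy in section 12.2.2 describe where the diary data come from. The pain-scale bullet in the same section also uses a weekly average, and Appendix 7 shows that there it means the past 7 days. If opioid use is read the same way, at the four Table 4 visits, each value is tied to surgery or radiation and nothing is re-mixed. This stands as a possible reading. However, section 13.4.2 does not adopt it, and its model would have no visit term even then. The patient random effect suggests several values per patient, but section 13.4.1 has the same wording for an endpoint with one value per patient, so it settles nothing.

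The second reply is that sign and size rest on invented profiles. That is correct, and the table shows both signs. The range is illustrative and not a bound.

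The third reply is that the shift is small beside the noise. The interval for oral use in section 2.6 (-1.2 to 21.1, 51 per group), treated as unpaired, implies a standard error of 22.3/(2 × 1.96) = 5.7 and an SD of 5.7/√(2/51), or about 29. With 20 per arm the standard error is 29 × √(2/20), or about 9 mg/day, so even 4.3 is under half of one. The 14 mg/day in section 2.6 is also only a loose yardstick: section 2.3 describes inpatient use, which the trial diary need not cover. All this lowers the urgency, but a systematic shift should not be left in when wording removes it.

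A reader might extend the argument to adverse events, because section 13.4 says "For categorical study variables the descriptive statistics will include counts, proportions and 95% binomial confidence intervals" and the celecoxib arm would be observed for less time. The documents do not support calling that an error. A crude proportion is a valid risk over the course actually given, and no between-arm test of adverse events is planned. Collection runs to the end-of-treatment visit, 1 to 30 days after the last radiation. At an equal constant hazard, and counting only time on therapy, 20% on placebo becomes 1 - 0.8^0.876 = 17.7% on celecoxib, and 50% becomes 45.5%. These gaps of 2.3 and 4.5 points compare with standard errors of 10.6 and 13.6 points at about 27 per arm.

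**Conclusion.** The point holds as a gap in specification with a predictable consequence. The plan neither names the opioid weeks to be analysed nor includes a term for time or phase, while the length and composition of the diary depend on the primary endpoint. Under the planned effect, celecoxib time on therapy is about 12% shorter and its radiation share rises from about 36% to 41%. These figures follow from section 13.2 and the assumed lead-in and radiation lengths. If the weekly values are pooled, the resulting shift is about -0.3 to +4.3 mg/day under the assumed profiles. It usually goes against celecoxib, because the days removed are late waiting days that probably have low use.

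A reader might infer that the plan's opioid comparison is biased whenever the drug works. That goes too far: pooling is allowed but not stated, a flat profile gives almost no shift, and visit-anchored values give none. The change is worth making because it is a better model than the one written down and uses data already collected.

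**What to change.** In sections 12.2.2 and 13.4.2, before unblinding, replace the single pooled opioid difference with two analyses:

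- **Before radiation:** weekly mean daily morphine equivalents by week since surgery, over a fixed window common to both arms. As an illustration, with normal start times and the section 13.2 figures, 95% of celecoxib patients would still be waiting at day 57.2 - 1.645 × 16.2 = 30.6, so a window of about four weeks would keep nearly everyone. State how weeks with unrecorded inpatient days are handled.
- **During radiation:** the same measure by week since its start.

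In each, include week (or visit) as a fixed effect alongside arm, provider and the patient random effect, and report a treatment contrast with its 95% confidence interval.

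The cost is SAP wording, a little more tabulation, and two opioid estimates instead of one, each somewhat less precise. No new data are needed. Adverse-event rates per patient-day or by phase could be added beside the proportions as an optional supplement, since start and end dates are already recorded (section 16.4.1).

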12.2.3 Functional Outcome

Functional outcomes will be compared between Arm 1 and Arm 2. Activity level will be assessed utilizing Karnofsky Performance Status and the use of G tube (yes or no) will be noted at every study visit. Patient-reported quality of life will be assessed by QLQ-H&N43 as indicated in the Schedule of Events. Swallowing capabilities, including food and liquid variety, will be captured through the use of a 7-point, Functional Oral Intake Scale as assessed by the treating investigator.

The number of days of adjuvant radiation missed or delayed will be retrospectively collected and compared between Arm 1 and Arm 2. Every day that treatment is delayed will be counted until the resumption of therapy.

12.3 Stopping Rules

While an interim analysis is not planned for this trial, continual safety monitoring will be provided by the DSMC. The study will be stopped if at any time the following *combination* of conditions occurs, which is: at least 2 patients undergoing study therapy experience grade

≥ 3 toxicities related to study drug resulting in discontinuation, *and* the proportion of patients experiencing these toxicities exceeds 15%. With this rule, if the true proportion of patients experiencing these toxicities is 2%, which is considered acceptable, the probability of stopping accrual is 0.03. If the true proportion of patients experiencing these toxicities is 20%, which is considered unacceptable, the probability of stopping accrual is 0.88.

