| Study Center | Single Site: Huntsman Cancer Institute |
| Objectives | 
Primary Objective: To assess the number of days from surgery to the initiation of radiation with the addition of celecoxib compared to placebo.
 
Secondary Objectives:
 
 - To assess overall pain control and management for patients on celecoxib compared to placebo. - To assess functional outcomes for patients on celecoxib compared to placebo. - To assess the effect of celecoxib therapy on Quality of Life (QoL) compared to placebo. - To assess the average number of treatment days missed during adjuvant radiation for patients on celecoxib compared to placebo. |
| Number of Subjects | 60 |
| Diagnosis and Main Eligibility Criteria | 
Inclusion Criteria:
 
 - Advanced-stage (overall stage III and IV) head and neck cancers (sinonasal, oral cavity, oropharynx, larynx, and hypopharynx) undergoing surgical resection and then adjuvant radiation. - Karnofsky Performance Status of ≥ 70 - Adequate organ function. 
Exclusion Criteria
 
 - Metastatic disease - Exclude patients with chronic kidney disease (stage 4 and 5), prior CVA or acute MI, chronic heart failure, prior episode of GI bleed or stomach or intestinal ulcer, and liver failure. |

Short Title: RESILIENCE

Version Date: 18APR2023

| | |
|-------------------------------------|---|
| | 
- Uncontrolled hypertension- Established in a pain management clinic or has taken opioids regularly for \geq 6 months. |
| Study Product, Dose, Route, Regimen | Celecoxib/placebo 200mg BID oral or via a feeding tube |
| Duration of administration | Celecoxib/placebo will be taken 1 to 7 days prior to surgery until the completion of adjuvant radiation, approximately 4 months total, maximum allowable time on the study is limited to 6 months. |
| Reference therapy | Placebo |
| Statistical Methodology | A mixed-effects regression model that accounts for clustering (patients nested within providers) to compare the average number of days from surgery to the initiation of radiation between treatment and control groups |

SCHEMA

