4.2 Randomization and Blinding

Patients who meet all criteria for enrollment will be randomly assigned to receive celecoxib (Arm 1) or placebo (Arm 2). Patients will be randomized through the OnCore system in a 1:1 ratio between Arm 1 and Arm 2 and stratified by treating provider.

To preserve the blind, only the Investigational Drug Services Pharmacy personnel at Huntsman Cancer Institute will know treatment assignments. Access to unblinded data/documents will be controlled by the pharmacy to ensure the blind is maintained. Every effort will be made to blind both the patient and the investigator to the treatment assignment, but the inadvertent unblinding of a patient may occur. If an investigator, site personnel, or patient is inadvertently unblinded, the unblinding will not be sufficient cause for the patient to be discontinued from study treatment or excluded from study analyses.

In the case of an emergency, the investigator has the sole responsibility for determining if the unblinding of a patient's treatment assignment is warranted. Patient safety must always be the first consideration in making such a determination. If the treating investigator decides that unblinding is warranted, the investigator should contact the investigational pharmacy for treatment assignment.

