4.3 Number of Patients

A total of 40 evaluable patients will be enrolled in this study with 20 patients randomized to each arm: 20 patients will receive celecoxib and 20 patients will receive placebo. It is expected that 25% of patients who start study therapy and undergo surgery will not start adjuvant radiation. Patients who do not start adjuvant radiation will be replaced. Taking this into account, it is estimated that 53 patients will be randomized to result in 40 evaluable patients.

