4.5 Study Duration

Based on current volumes, it is proposed that this study can be completed within 2 years of initiation.

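### Section 12.3 states a 0.88 stopping probability that fits monitoring of about one arm, but it names no arm or maximum N, and the protocol provides no one-arm count

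*Combined protocol and SAP*

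**What the plan says.** Section 12.3 stops the study when two conditions hold together. The first is that "at least 2 patients undergoing study therapy experience grade" 3 or higher "toxicities related to study drug resulting in discontinuation"; the second is that the proportion with such toxicities is above 15%. The rule applies at any time, with no formal interim analysis. Stopping probabilities are 0.03 at a true rate of 2% and, at the other end, "If the true proportion of patients experiencing these toxicities is 20%, which is considered unacceptable, the probability of stopping accrual is 0.88".

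Other sections bear on how the rule would be run:
- Section 4.2: 1:1 randomization, and "only the Investigational Drug Services Pharmacy personnel at Huntsman Cancer Institute will know treatment assignments". The next sentence puts access to unblinded material under pharmacy control.
- Section 4.3: 40 evaluable patients, 20 per arm, and "it is estimated that 53 patients will be randomized to result in 40 evaluable patients". The Study Summary has "Number of Subjects | 60".
- Section 7.1: patients take celecoxib or placebo. Section 13.3.1: one dose of study therapy makes a patient evaluable for toxicity; no arm is named.
- Section 13.2.1: the sample size calculation was modified during the trial.
- Section 16.3: the DSMC reviews SAEs monthly, receives a summary that covers stopping rules, and works under a DSM plan that is not part of these documents. Concern on the part of the DSMC or the principal investigator can also stop the study.

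**The concern.** A stopping probability has meaning only for a stated group of patients and a stated maximum number. Section 12.3 gives neither, and the documents offer several candidates: 20 per arm, 26 or 27 per arm, 30 per arm, 40, 53 or 60. The choice changes both the stated probability and the number of events that triggers the rule. This is the only numerical study-level safety boundary in the document. If the figures were computed for one arm and the committee counts over both, the protection differs from what section 12.3 tells the IRB and the DSMC.

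**Working it through.** **Inputs.** From 12.3: stop if the count x is at least 2 and x/n > 0.15, checked at any time; true rates 2% and 20%; stated results 0.03 and 0.88. From 4.3 and the Study Summary: totals of 40, 53 and 60, hence arms of 20, 26 or 27, and 30.

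**Method.** Let P(n, x) be the probability of x events among the first n patients without having stopped. Then P(n, x) = (1 − p)·P(n−1, x) + p·P(n−1, x−1). Whenever x ≥ 2 and x/n > 0.15, that probability is moved to the stopped total. The result is exact if each outcome is known before the next patient is counted.

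**Reproducing the stated pair.**

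| Maximum N | Candidate | P(stop) at 2% | P(stop) at 20% |
|---|---|---|---|
| 20 | evaluable arm | 0.028 | 0.833 |
| 26, 27 | arm of 53 | 0.029 | 0.879 |
| 28 | – | 0.029 | 0.882 |
| 30 | arm of 60 | 0.029 | 0.890 |
| 40 | evaluable total | 0.029 | 0.924 |
| 53 | randomized total | 0.029 | 0.950 |
| 60 | Study Summary total | 0.029 | 0.956 |

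To two decimals, 0.88 appears only for N = 26 to 28. Allowing two percentage points admits N = 25 to 31 (0.869 to 0.896).

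The 0.03 does not discriminate. Two events trigger the rule only up to n = 13 (2/13 = 15.4%, 2/14 = 14.3%), and at 2% almost all stopping happens there: 1 − 0.98^13 − 13 × 0.02 × 0.98^12 = 1 − 0.769 − 0.204 = 0.027. Every N from 20 to 60 therefore rounds to 0.03.

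Batched or delayed looks do not rescue a pooled total. At N = 40, looks every 5 patients give 0.017 / 0.883 and every 12 give 0.024 / 0.887. No such schedule tried at 40, 53 or 60 gave 0.03 and 0.88 together.

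**The boundary at 53 randomized.** This step needs no assumed rates. One arm of 26: 4/26 = 15.4%, so 4 events suffice. With 27 in the arm, 4/27 = 14.8% does not meet the rule and 5/27 = 18.5% does. Pooled: 7/53 = 13.2% does not, 8/53 = 15.1% does. If no placebo patient has an event, 8 pooled events are 8/27 = 29.6% or 8/26 = 30.8% of the celecoxib arm.

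**Pooled use, two meanings of 20%.** If 20% is the pooled rate, the probability is 0.92, 0.95 or 0.96, and 0.88 is too low. If 20% is the celecoxib rate and q the placebo rate, the pooled rate under 1:1 allocation is (0.20 + q)/2. The documents give no q, so the values below are assumptions; N = 53.

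| Assumed q | Pooled rate | P(stop) |
|---|---|---|
| 0% | 10% | 0.50 |
| 2% | 11% | 0.57 |
| 5% | 12.5% | 0.67 |
| 10% | 15% | 0.80 |

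For N = 53 the pooled probability reaches 0.88 only at q of about 14%.

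**The case against.** The strongest reply is that the rule is already a one-arm rule. Relatedness to study drug points to celecoxib, section 13.1 uses study therapy in the sense of the active drug, and the arithmetic then works. Section 4.2 also contemplates controlled access to unblinded material, and the DSM plan may settle the matter. This stands as far as it goes: a one-arm reading is possible and no arithmetic error follows from it. But the N is still unstated, no provision sends counts by arm to the DSMC, and a blinded investigator can attribute an event in a placebo patient to study drug.

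Second, a reader might infer that the denominator is missing altogether. It is not: section 13.3.1 supplies a toxicity population. What is missing is the arm and the maximum N.

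Third, a reader might infer from 0.50 to 0.80 that 0.88 overstates protection. Section 12.3 speaks of the true proportion of patients; if that is the pooled proportion, 0.88 understates it. The lower values hold only if 20% is the celecoxib rate, and they rest on placebo rates that the documents do not give.

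Fourth, the match to one arm assumes immediate outcomes. Treatment lasts "approximately 4 months total, maximum allowable time on the study is limited to 6 months", and "it is proposed that this study can be completed within 2 years of initiation". A simulation with even entry over 24 months and events spread over 4 months (both patterns assumed) gives about 0.02 / 0.84 to 0.86 for one arm of 26 to 28, and 0.018 / 0.89, 0.015 / 0.92 and 0.013 / 0.92 for pooled totals of 40, 53 and 60. On those assumptions neither reading yields the stated pair, so the inference to one arm is conditional.

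Finally, the safeguards in section 16.3 are real, and the 4-against-8 contrast applies at full enrolment. Both lessen the practical risk; neither says which count applies.

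**Conclusion.** The point holds as a mismatch between a stated operating characteristic and the rule as the protocol lets it be run. With immediate outcomes, 0.88 describes 26 to 28 patients (25 to 31 within two points) and none of the pooled totals of 40, 53 or 60. The protocol provides no route to a one-arm count. If the rule is run pooled, 0.88 is too low when 20% is the pooled rate, and the boundary at 53 randomized moves from 4 of 26 to 8 of 53.

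Confidence is high that the arm and N are unstated, and moderate that pooled use is what the text implies. Three stronger conclusions are not supported. 0.88 is not shown to be a miscalculation. Pooled monitoring is not compelled by the text. And although the sample size was modified (13.2.1), nothing shows that the probabilities belong to a superseded N; the 26 to 28 is back-calculated, and only the sponsor can confirm what was used.

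**What to change.** Leave the 2-patient and 15% thresholds as they are and reconcile sections 4.2, 12.3 and 13.3.1 by one of two routes.

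(a) Within arm. State in 12.3 that the rule is evaluated in the celecoxib arm among patients in the 13.3.1 toxicity population, and give the sponsor-confirmed maximum N behind 0.03 and 0.88. Amend 4.2 so that the pharmacy supplies counts by arm to a closed DSMC session. Cost: one or two sentences in 12.3, one in 4.2, and a closed table; DSMC members would see counts by arm while the study team stays blinded.

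(b) Pooled. State that the rule runs over the whole 13.3.1 population, and replace 0.88 with pooled probabilities at the stated N over a declared range of placebo rates, including both arms at 20%. Cost: one or two sentences; the stated figure is less favourable when placebo toxicity is low.

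Under either route, say whether outcomes are assumed known before the next patient is counted, and confirm that the figures match the current sample size. No new patients or data are needed.
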